4 STATISTICAL CONSIDERATIONS

4.1 Study Outcomes

The study outcomes are listed below.

The primary outcomes are:

- Brain PWV
- Brachial-femoral PWV

Note: All power calculations for this protocol are based on measures from PWV

The secondary outcomes are:

- Executive function
- Neurovascular coupling
- Carotid-femoral PWV
- Augmentation index
- Femoral-ankle PWV

Mechanistic and descriptive outcomes are:

- Cerebral perfusion
- Total brain blood flow
- Middle cerebral artery velocity
- Static cerebral autoregulation
- Baroreflex sensitivity
- Heart rate variability
- Heart rate
- Peripheral diastolic blood pressure
- Peripheral systolic blood pressure
- Tissue saturation index
- Venous pooling in the gastrocnemius
- Bouts of physical activity
- Sleep duration

4.2 Statistical Analysis

All statistical procedures will be completed with SPSS Statistics version 25.0 (SPSS, IN., Durham, NC, USA) and Jamovi v0.9 (Jamovi, UK). The α -level will be set a prior at 0.05 for all statistical procedures. Descriptive statistics and mechanistic outcomes will be collected to compare similarities amongst the sample group and to eliminate the potential for extraneous covariates. Answering the research question will require a linear multi-level mixed model. Statistical models will observe for changes in the primary and secondary outcomes within conditions (Baseline, Post-PS, Post-MS) and between conditions (CON vs. SMS at similar time points). Mechanistic outcomes will also be used to assist in discussions of physiological responses to MS and PS. Effect sizes will be calculated as Cohen's d , where <0.20 is considered to be a small, > 0.20 to < 0.50 a moderate, and > 0.60 a large effect. For the mixed models Cohen's d will be calculated as the effect of condition (β) or time (β) from linear mixed models divided by the baseline SD. Raw data will be presented as mean [standard deviation] and mixed model data are presented as mean [95% confidence interval].

4.3 Tabulation of Results

Mean and variance will be tabulated after raw measures taken in triplicate are entered into a lab-created template.

Table 4. Methods to describe result summarization for this experimental protocol.

Abbreviations: X, Mean/SD will be calculated for this result; 1, Measure is reported as a single value from each experimental visit; n/a, Measure is not being taken at this timepoint.

Device	Outcomes	Baseline		Post-PS		Post-MS	
		X	SD	X	SD	X	SD
VICORDER®	bfPWV	X	X	X	X	X	X
	cfPWV	X	X	X	X	X	X
	faPWV	X	X	X	X	X	X
	CBPs	X	X	X	X	X	X
	Peripheral BPs	X	X	X	X	X	X
	Augmentation index	X	X	X	X	X	X
TCD	Brain PWV	X	X	X	X	X	X
	MCA velocity	X	X	X	X	X	X
	Static cerebral autoregulation	X	X	X	X	X	X
	Neurovascular coupling	X	X	X	X	X	X
NIBP	Baroreflex sensitivity	X	X	X	X	X	X
	Heart rate variability	X	X	X	X	X	X
	Heart rate	X	X	X	X	X	X
Ultrasound	Cerebrovascular BF	1	X	1	X	1	X
NIRS	Cerebral perfusion	X	X	X	X	X	X
	Tissue saturation index	X	X	X	X	X	X
	Venous pooling	X	X	x	X	x	X
Cognitive Tests	Executive Function	n/a	n/a	n/a	n/a	1	X

4.4 Missing Values

Subjects with missing data will be included in the analysis. The linear mixed-effects model is well-designed for coping with incomplete longitudinal data. Reasons for non-complete data sets will be recorded, and available values will be compared against the population estimates to ascertain risk of bias.

4.5 Quality Control

For a given outcome all measurement and analysis will be conducted by a single observer. At the start of the study, the first three sets of data collected by the first three research participants will be checked by an independent observer.

At the conclusion of the study, a random selection of 10% of the data sets (e.g., all data from 2 participants) will be re-scored by an independent observer and used to calculate inter-observer reliability.

4.6 Sample Size

Calculations to determine minimum sample size will be based on central vascular health outcome, aortic pulse wave velocity (PWV). We will conduct a power calculation based on reported normal values for the primary outcome, central PWV. Healthy people aged 40-49 maintain an average PWV of 7.5 m/s. For the current study, we will opt to sample based on a conservative change score of 1 m/s. We will also use a conservative usual error of 1.25 m/s based on reported data. Using magnitude-based inference, to estimate the sample size required to detect the smallest detrimental (or beneficial) effect in a cross-over study, with the maximum chances of a type 1 and 2 error set at 5% (i.e. very unlikely), approximately eighteen participants will be required.

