Participants will arrive to the Applied Physiology Laboratory (APL) between 6:00 and 10:00 AM fasted (for Visit 3: 2-5 days following the Visit 2). Participants will be fasted and refrain from caffeine intake for at least 12 hours, and alcohol and strenuous physical activity for at least 24 hours prior to arrival. Upon arrival, height and weight will be recorded followed by 10 minutes of quiet rest in the supine position (white solid boxes in **Figure 1**). During these 10 minutes, the subject will be fitted with a NIRS probe on the prefrontal cortex and medial gastrocnemius. The NIBP, TCD, and VICORDER® devices will also be affixed to the participant during this time period during this time. Sitting periods (solid gray boxes in **Figure 1**) will begin for both conditions once all devices are attached to the participant, the subject is shifted to an upright seated position, and at least 10min of supine rest has been recorded. During the CON visit, subjects will undergo a brief 20min sitting period. For the SMS condition, subjects will be asked to sit still and quietly for 2 hours while watching a non-stimulating documentary. Each condition will receive the MS (black boxes in **Figure 1**) at the conclusion of the sitting periods in both CON and SMS. After exposure to the MS in both conditions, data collection procedures for this protocol will be completed for VICORDER® immediately after the MS and every 5 minutes for 25 minutes (See **Figure 1** for visual details on how and when data is being collected). Brain BF will be assessed by US 20 minutes post-completion of the MAT. Finally, a battery of cognitive tests (Verbal Fluency Test and Trails A+B tests) will be administered to the participant (boxes with diagonal shades in **Figure 1**).

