2.4 Experimental Procedures

[figure not shown]

Figure 2. A visualization of the experimental protocol. Maintenance of external validity for this study will require exposure of the MS to be time-matched between both experimental conditions. The use of accelerometry will allow investigators to observe physical activity and sleep patterns to ensure uniformity in pre-assessment behaviors. All time points are expressed relative to the time of completion of the mental stressor. **Abbreviations:** BF, blood flow; PWV/A, Pulse wave velocity & analysis; (1), collection of PWV/A for the primary outcome, bfPWV/A will be collected at this time point only; (3) collection of PWV/A for bfPWV, cfPWV, and faPWV; PA, Physical activity; t, time; NIRS, Near-infrared spectroscopy; NIBP, Non-invasive blood pressure; TCD, Transcranial Doppler.

Protocol 1: Mental Arithmetic Test

Test Structure					Application																																																																																																																																																																																																		

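### The 5% type 2 error claimed in section 4.6 does not carry over to two-sided 95% intervals as planned in section 4.2 (power about 92% at n=20), and the outcome it names matches neither listed primary by name

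*Combined protocol and SAP*

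**What the plan says.** Section 4.6 (Sample Size) starts from aortic PWV and then states: "We will conduct a power calculation based on reported normal values for the primary outcome, central PWV". Its inputs are a normal value of 7.5 m/s, an effect ("For the current study, we will opt to sample based on a conservative change score of 1 m/s") and an error term ("We will also use a conservative usual error of 1.25 m/s based on reported data"). The method is given as "Using magnitude-based inference, to estimate the sample size required to detect the smallest detrimental (or beneficial) effect in a cross-over study", and the result is that "with the maximum chances of a type 1 and 2 error set at 5% (i.e. very unlikely), approximately eighteen participants will be required". The planned enrolment is 20 (Synopsis and section 2.1).

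Section 4.2 (Statistical Analysis) plans a multi-level linear mixed model with alpha 0.05, compares CON with SMS at matching time points, and reports model results with 95% confidence intervals. It does not mention magnitude-based inference, and neither section states whether tests are one- or two-sided.

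The primary outcomes in the Synopsis, Table 1, Table 2 and section 4.1 are brain PWV and brachial-femoral PWV (bfPWV). Section 4.1 adds only this on power: "Note: All power calculations for this protocol are based on measures from PWV".

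**The concern.** A sample-size statement should describe the analysis that will be run, on an outcome that the plan lists. Section 4.6 appears to fail on both counts. Its error rates come from a framework that the analysis section does not use and for which the documents give no formula or decision rule. Its outcome, aortic or central PWV, is not a name on the list of primaries. If the 5% type 2 error does not apply to the planned intervals, a null result would be read against a stronger assurance than the design gives. A reader also could not tell which primary outcome the assurance covers.

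**Working it through.** **Inputs.** Difference to detect: 1 m/s (section 4.6). Error term: 1.25 m/s (section 4.6), taken here as the SD of the paired CON–SMS difference; this is an assumption, because section 4.6 does not define the term. Type 1 and type 2 error: 5% each (section 4.6). Alpha 0.05 with 95% intervals (section 4.2). Sample sizes: 18 (section 4.6) and 20 (section 2.1). A paired t test stands in for the mixed-model contrast at a single time point.

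**Step 1: reproduce the plan's 18.** Normal formula: n = [SD × (z for type 1 + z for type 2) / difference]².

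- One-sided 5%: [1.25 × (1.645 + 1.645) / 1]² = 16.9, so 17. The exact noncentral-t calculation gives 19. The stated 18 lies between the two.
- Two-sided 5%: [1.25 × (1.960 + 1.645) / 1]² = 20.3, so 21. The exact calculation gives 23.

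**Step 2: power at the stated and planned sizes.** The noncentrality is √n × 1 / 1.25, which is 3.39 at 18 and 3.58 at 20. Noncentral-t power on n − 1 degrees of freedom:

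| SD of difference 1.25 m/s | n = 18 | n = 20 | n for 95% power |
|---|---|---|---|
| One-sided 5% | 94.6% | 96.4% | 19 |
| Two-sided 5% | 89.2% | 92.4% | 23 |

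The two-sided type 2 error is therefore 100 − 89.2 = 10.8% at 18 and 100 − 92.4 = 7.6% at 20. Giving up one degree of freedom for a period term changes little: two-sided power becomes 89.0% and 92.2%.

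**Step 3: sensitivity to the meaning of the error term.** Suppose 1.25 m/s is instead the error of one recorded value, with independent errors in the two conditions. The SD of the difference is then √2 × 1.25 = 1.77 m/s. Two-sided power falls to 61.9% at 18 and 67.0% at 20. On this reading 95% power needs 34 (normal) or 36 (t) one-sided, and 41 or 43 two-sided, so it does not reproduce 18.

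**Step 4: the outcome name.** Section 4.6 attaches the words primary outcome to central PWV. The Figure 2 legend in section 2.4 attaches them to bfPWV: "collection of PWV/A for the primary outcome, bfPWV/A will be collected at this time point only". The Synopsis rationale divides arterial stiffness into peripheral, central and cerebral. Brain PWV is plainly the cerebral measure, which leaves bfPWV as the natural meaning of central PWV among the two primaries. No sentence makes that link, and none ties the 7.5, 1 and 1.25 m/s inputs to bfPWV or to brain PWV.

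**The case against.** The strongest reply is that nothing has been mis-sized. The 18 is recovered by a standard one-sided calculation, and the trial recruits 20, where one-sided power is 96.4%. The Synopsis hypothesis is directional. The 95% intervals in section 4.2 are a reporting format and not a declared decision rule, so two-sidedness is inferred. The study is labelled a pilot and its aims are exploratory. A conventional test also cannot refute a magnitude-based calculation whose rule is not given.

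Much of this stands. There is no arithmetic error, sidedness is unclear and not contradicted, and the magnitude-based figure cannot be checked from the documents. Two things remain. Section 4.6 itself refers to effects in either direction, detrimental or beneficial, which sits better with a two-sided reading. And whatever the sidedness, the stated error rates belong to a framework that section 4.2 does not use, so they do not describe the planned analysis.

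On the outcome, a reader might infer that the trial was sized on a secondary measure such as carotid-femoral PWV. The documents do not support that: section 4.6 calls its outcome primary, and bfPWV is the likelier referent. What they show is inconsistent naming.

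**Conclusion.** The concern holds as a mismatch between the sample-size statement and the planned analysis, together with an outcome name that matches neither listed primary. If inference is by the 95% intervals, the claimed 5% type 2 error becomes about 11% at 18 and about 8% at 20. The shortfall against 95% power is 5.8 and 2.6 percentage points. This rests on three assumptions: a two-sided test, 1.25 m/s as the SD of the CON–SMS difference, and a paired t test as an approximation to the mixed model.

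A reader might go further and call the trial underpowered, citing the 62% to 67% figures. The documents do not support that. Those figures need a meaning of 1.25 m/s that cannot produce the plan's own 18, and 92% at the planned size is good power. They belong in the text only as a caveat until the error term is defined. Nor do the documents show that power for brain PWV was never considered; they show only that no calculation for it is reported.

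**What to change.** Keep n=20 and reword section 4.6:

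- Replace the magnitude-based 5%/5% claim with the power of the section 4.2 analysis. That is about 92% two-sided at n=20 for a 1 m/s difference, if 1.25 m/s is the SD of the CON–SMS difference. If a one-sided test is intended, say so in both sections and give 96%.
- Name the listed primary outcome that the calculation covers (bfPWV, if that is meant).
- Say that no power calculation is reported for brain PWV.
- Say what 1.25 m/s measures. If it is the error of a single value with independent errors, two-sided power at 20 is about 67%, and the text should give that figure instead.

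The cost is a rewritten paragraph and one sentence on sidedness in section 4.2. No participants, measurements or analyses are added. The only downside is a slightly less favourable stated power if 1.25 m/s is the SD of the difference.

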4.7 Statistical Support

Statistical expertise, study coordination and statistical computations for research database management (RDM) and data analysis will be provided by the research team. Advised by [name]. If needed, the faculty advisor will submit a request to NCTracs.

5 Participant Screening, Withdrawal & Completion5 n failure procedures

Participants will not be able to participate if they do not meet the inclusion criteria. The acceptability of participants' potential recordings from each device will be made during the familiarization visit.

5.2 Participant withdrawal

If a participant decides to withdraw from the study all efforts should be made to complete and report study assessments as thoroughly as possible. The investigator will contact the participant by telephone or through a personal visit to establish the reason for the study withdrawal. A complete final evaluation at the time of the patient's study withdrawal should be made with an explanation of why the patient is withdrawing from the study. If the reason for removal of a patient from the study is an adverse event, the principal specific event will be recorded on study data collection forms. If the reason for withdrawal or removal is not an adverse event, the nature of the reason will be recorded on the study data collection forms.

5.3 Participant Completion

Upon completion of the study, participants will be thanked, and the results discussed.

6 SAFETY MONITORING & MANAGEMENT

6.1 Adverse Event Risk

Investigators leading this project are knowledgeable of clinically healthy values for BP, cardiac output, and other experimental outcomes. It is anticipated the collection of values of clinical concern will be rare as those with a diagnosis of cardio-metabolic diseases will be excluded from this study entirely. However, in the event of clinically meaningful cardiovascular values, the participant will be notified of his or her results and consultation with faculty advisor, [name] will be completed on further action, if needed. It is ultimately the decision of the subject to follow through with action after gaining knowledge and receiving advice on his or her unfavorable cardiovascular health.

The devices used in this study are noninvasive. There are no known severely adverse events that have occurred with use of the stated devices.

VICORDER® - The system requires the placement of pressure cuffs over several arteries for the collection of PWV/A data. Pressure cuffs will only be inflated underneath a level of 65 mmHg. Physical harm or discomfort is unlikely and include, but are not limited to:

- Risk 1: Discomfort/unease: Infrequent (1 – 10%) – Application of a slight pressure over the carotid artery may impose a sense of unease for the participant. However, the light pressure used for this experimental protocol will in no way significantly damage cardiovascular structure or place the participant in danger. Investigators will make certain that communication on the procedures during testing session are clearly conveyed to the participant for comfort and safety.

Near-infrared spectroscopy (NIRS): Risk of injury or discomfort is extremely low due to this device. Possible physical harms are, but not limited to:

- Risk 1: Eye damage/irritation: Rare (<1%) – Please do not, at any point, stare into the light emitted from the NIRS probe
- Risk 2: Skin heating and irritation: Rare (<1%) – Wearing the NIRS probe for extended periods of time at once can theoretically lead to a warm feeling at the area where the probe is placed. However, this risk is minimal because the light emitted from this probe is not powerful enough to heat the skin. If you let the investigators know of any discomfort due to the probe, we will follow manufacturer guidelines to ensure the device is functioning correctly.

Transcranial Doppler (TCD): Data collection from this system requires the affixation of a headpiece to the participant. Risk of injury due to this device is extremely low. Possible harms may include, but are not limited to:

- Risk 1: Mild headache: Infrequent (1 – 10%) – High quality data from this device requires the placement of the probe over the middle cerebral artery (MCA) and posterior

cerebral artery (PCA). The slight pressure applied to the area may be slightly discomforting and unusual for the participant.

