8.4	Efforts to ensure equal access to participation among women and minorities	42
9	STUDY MANAGEMENT/ CONSENT	43
9.1	Consent and Institutional Review Board (IRB) Approval.....	43
9.2	Efforts to Minimize Influencing the Participant's Decision to Participate	43
9.2	Required Documentation	43
9.3	Adherence to the Protocol.....	43
9.4	Emergency Modifications	43
10	REFERENCES	44

ABBREVIATIONS

ABBREVIATION	DEFINITION
ADRD	Alzheimer's Disease and Related Dementia
AIx	Augmentation Index
APL	Applied Physiology Laboratory
BF	Blood Flow
bfPWV	Brachial-Femoral Pulse Wave Velocity
BP	Blood Pressure
CBP	Central Blood Pressure
cfPWV	Carotid-Femoral Pulse Wave Velocity
cm	Centimeters
CON	Control Experimental Session
CONSORT	Consolidated Standards of Reporting Trials
CV	Cardiovascular
CVD	Cardiovascular Disease
CVH	Cardiovascular Health
CVS	Cardiovascular System
cwNIRS-SRS or NIRS	Continuous Wave Near-Infrared Spectroscopy
DBP	Diastolic Blood Pressure
ECG	Electrocardiogram
EF	Executive Function
faPWV	Femoral-Ankle Pulse Wave Velocity
HIPAA	Health Insurance Portability and Accountability Act
HR	Heart Rate
hr	Hours
HRV	Heart Rate Variability
ID	Identification Number
IRB	Institutional Review Board
kg	Kilograms
L	Straight-line length or distance
m/s	Meters per second
MAT	Mental Arithmetic Test
MCA	Middle Cerebral Artery
MCAv	Middle Cerebral Artery Velocity
min	Minutes
mmHg	Millimeters of Mercury
MS	Mental Stress or Mental Stressor
N/A	Not Available
NIBP	Non-Invasive Blood Pressure
PA	Physical Activity
PCA	Posterior Cerebral Artery
PHI	Personal Health Information

PI	Principal Investigator
PPG	Photoplethysmography or Photoplethysmography
PS	Prolonged Sitting
PWA	Pulse Wave Analysis
PWV	Pulse Wave Velocity
PWV/A	Pulse Wave Velocity and Analysis
RDM	Research Database Management
SBP	Systolic Blood Pressure
SD	Standard Deviation
sec or s	Seconds
SMS	Sitting & Mental Stress Experimental Session
TCD	Transcranial Doppler
tHb	Total Hemoglobin
TMT	Trails Mental Tests or Trails A + B
TSI	Tissue Saturation Index
TT or ΔT	Transit Time
UNC	University of North Carolina at Chapel Hill
US	Ultrasound
VFT	Verbal Fluency Test
VPN	Virtual Private Network
X	Mean or Average

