2.5 Measurements

Table 2. Summarization of measures used for the protocol, “The Combined Effects of Prolonged Sitting and Mental Stress on Vascular and Cerebrovascular Function in Middle-Aged Adults”. Each experimental variable is listed under the “Outcomes” column with its designation as either a primary, secondary, or mechanistic measure listed under the “Role Classification” column. The “Device” column names the equipment used to collect the data. **Abbreviations:** TCD, Transcranial Doppler; CON, Control condition; SMS, Sitting mental stress condition; VFT, Verbal fluency test; TMT, Trail making test; NIRS, Near-infrared spectroscopy; cwNIRS-SRS, Continuous-wave near-infrared spectroscopy. Minute values are expressed relative to the administration of the MAT.

Outcomes	Device	Unit	Time Period (min)			Role Classification
			Condition	Time Periods (min)	Measurements Taken	
Brain Pulse Wave Velocity	TCD	meters per second (m/s)	CON	Continuous	1	Primary
			SMS	Continuous	1	
Brachial-femoral Pulse Wave Velocity (PWV)	VICORDER®	meters per second (m/s)	CON	-5, 0, 5, 10, 15, 20, 25	7	Primary
			SMS	-115, -15, 0, 5, 10, 15, 20, 25	8	
Executive Function	VFT/ TMT	Cognitive performance: measured in seconds (s)	CON	25	1	Secondary
			SMS	25	1	
Neurovascular Coupling	NIRS/ TCD	Unitless: relationship between local neural activity and subsequent changes in cerebral blood flow. [CITE]	CON	Continuous	1	Secondary
			SMS	Continuous	1	
Augmentation Index (Aix)	VICORDER®	Percentage. It is defined as the difference between the second and first systolic peaks (P2-P1) expressed as a percentage of the pulse pressure ^{24,25}	CON	-5, 0, 5, 10, 15, 20, 25	7	Secondary
			SMS	-115, -15 0, 5, 10, 15, 20, 25	8	
Carotid-femoral PWV	VICORDER®	meters per second (m/s)	CON	-5, 25	2	Secondary
			SMS	-115, -15, 25	3	
Central Blood Pressures (CBP)	VICORDER®	Millimeters of Mercury (mmHg)	CON	-5, 0, 5, 10, 15, 20, 25	7	Secondary
			SMS	-115, -15 0, 5, 10, 15, 20, 25	8	
Femoral-ankle PWV	VICORDER®	meters per second (m/s)	CON	-5, 25	2	Secondary
			SMS	-115, -15, 25	3	
Physical Activity	ActiGraph	Minutes. Activity data will be classified as either "Light", "Moderate", or "Vigorous".	CON	Continuous	1	Mechanistic
			SMS	Continuous	1	
Sleep Duration	ActiGraph	Minutes.	CON	Continuous	1	Mechanistic
			SMS	Continuous	1	
Cerebral Perfusion	cwNIRS-SRS	Relative changes in total hemoglobin concentration (tHb). Expressed as a percentage.	CON	Continuous	1	Mechanistic
			SMS	Continuous	1	

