Cerebrovascular Blood Flow	Doppler Ultrasound	meters per second (m/s)	CON	-5, 20	2	Mechanistic
			SMS	-120, -5, 20	3	
Middle Cerebral Artery Velocity	TCD	Centimeters per second (cm/s)	CON	Continuous	1	Mechanistic
			SMS	Continuous	1	
Static Cerebral Autoregulation	TCD	Unitless. Refers to MAP and CBF under steady state conditions that can be observed over a period of time ²⁶	CON	Continuous	1	Mechanistic
			SMS	Continuous	1	
Baroreflex Sensitivity	NIBP	Sensitivity: BRS is defined as the change in heart rate variability in milliseconds per unit change in BP	CON	Continuous	1	Mechanistic
			SMS	Continuous	1	
Heart Rate Variability (HRV)	NIBP	milliseconds (ms)	CON	Continuous	1	Mechanistic
			SMS	Continuous	1	
Heart Rate	NIBP	Beats per minute	CON	Continuous	1	Mechanistic
			SMS	Continuous	1	
Peripheral blood pressures (SBP, DBP)	VICORDER®	Millimeters of Mercury (mmHg)	CON	-5, 0, 5, 10, 15, 20, 25	7	Mechanistic
			SMS	-115, -15 0, 5, 10, 15, 20, 25	8	
Tissue Saturation Index	cwNIRS-SRS	Relative changes in TSI. Data will be presented as percent changes.	CON	Continuous	1	Mechanistic
			SMS	Continuous	1	
Venous Pooling in the Gastrocnemius	cwNIRS-SRS	This is a physiological response to prolonged sitting. It is quantified using the NIRS-SRS device by recording levels of tHb at the gastrocnemius	CON	Continuous	1	Mechanistic
			SMS	Continuous	1	

DEVICE 1: VICORDER®

PWV is calculated by dividing arterial path length (L) by the pulse transit time (TT) between a proximal and distal arterial segment. Measurements for L are acquired by recording the straight line distance between the proximal and distal cuff, per manufacturer guidelines. For PWV measures including the carotid artery, the straight line distance from the carotid artery to the sternal notch is included in calculations for L.

Transit time is calculated by the Vicorder software's proprietary algorithm that measures the time between the foot of the proximal pressure waveform to the foot of the distal pressure waveform. Pressure waveforms will be simultaneously captured using volume displacement cuffs. A small balloon cuff is placed over the carotid artery. The balloon used to generate the carotid pulse wave does not cause discomfort as it inflates to sub-diastolic blood pressure (~50 mmHg).

DEVICE 2: Transcranial Doppler

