3 MEASUREMENT DEVICES

[figure not shown]
[figure not shown]
Device 1: VICORDER®

Device		
 Company: SMT Medical Model: VICORDER®: Arterial Stiffness Model Location: Wurzburg, Germany Oscillometric cuffs inflate at sub-systolic pressures to detect changes in the pressure waveform. Different sized cuffs are available.
Example Set-up		
 The cuffs can be placed on any 2 arterial segments. In the figure to the left, pressure cuffs placed over the brachial and femoral arteries. A small balloon is placed over the carotid artery to obtain a measurement for cfPWV. A low pressure (50 mmHg) is used for this site with minimal discomfort.
Raw Data		
 Top display = pressure waveform from proximal arterial segment Bottom display = pressure waveform from distal arterial segment Intrinsic software automatically detects the foot of the waveform of each arterial segment
Data Analysis		
 A = Site of proximal artery B = Site of distal artery Pulse wave velocity (PWV) = distance (D) / transit time (TT) Straight line distance (L) = Distance between two cuffs as measured according to manufacturer guidelines

[figure not shown]
[figure not shown]
		
 Transit Time (ΔT or TT) = Time between foot of proximal and distal waveforms. Oscillometric pressure waveforms will be determined at the brachial artery of the non-dominant arm using the VICORDER® in order to determine brachial and central arterial blood pressures.
Data Reduction		
 L is plugged into software prior to measurement. TT is averaged across 3 waveforms, and used to calculate one PWV Process repeated 3 times, for 3 PWVs per measurement cycle. Closest 2 PWVs averaged and used as outcome for measurement cycle.

[figure not shown]
Device 2: Transcranial Doppler (TCD)

Device		
 Company: Compumedics DWL Model: Transcranial Doppler Sonography TCD Location: Charlotte NC, USA DiaMon headset can be adjusted in 3 ways to accommodate each individual Connection between rear band and side panel sits behind the ear, below the occipital bone to ensure signal TCD probes should be in contact with head if headset has been fitted correctly

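### Section 6.1 keeps VICORDER cuffs below 65 mmHg, yet brachial and central blood pressures are taken from that same device; the passages must be reconciled

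*Combined protocol and SAP*

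**What the plan says.** On cuff pressure:

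- Section 6.1 introduces the VICORDER risk with "The system requires the placement of pressure cuffs over several arteries for the collection of PWV/A data" and continues "Pressure cuffs will only be inflated underneath a level of 65 mmHg". No use of the device is exempted. The abbreviation list expands PWV/A as "Pulse Wave Velocity and Analysis", so the term covers pulse wave analysis as well as velocity.
- The Device 1 entry in section 3 says "Oscillometric cuffs inflate at sub -systolic pressures to detect changes in the pressure waveform". It gives no figure for these cuffs.
- For the carotid balloon, sections 2.5 and 3 give about 50 mmHg, which fits the limit.

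On blood pressure:

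- The same Device 1 entry says that oscillometric waveforms "will be determined at the brachial artery of the non-dominant arm using the VICORDER", and gives the purpose as obtaining brachial and central arterial pressures.
- Table 2 lists peripheral SBP and DBP (mechanistic) and central pressures (secondary) with VICORDER as the device. Both are scheduled at -5, 0, 5, 10, 15, 20 and 25 min in CON and at -115, -15, 0, 5, 10, 15, 20 and 25 min in SMS. Table 3 repeats the schedule.
- The synopsis also names central pressures as secondary. Table 1 and section 4.1 do not list them.

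**The concern.** The safety section and the measurement schedule describe the same device in ways that cannot both hold. A cuff reading of systolic pressure requires the cuff to reach systolic pressure, and the limit as written rules that out.

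Two things are at stake. If staff follow the limit literally, the brachial pressures are largely unobtainable and the central pressures have no scale in mmHg. Section 6.1 also relies on BP when it promises to tell participants about clinically meaningful values. If staff inflate further to get the readings, the risk text is incomplete: the only VICORDER risk it lists is unease from slight pressure over the carotid artery, and it does not mention a brachial inflation above the stated ceiling.

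**Working it through.** The plan gives no figure to reproduce here. The check sets the passages side by side and counts the affected measurements.

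**1. What the limit covers.** It follows directly on the sentence about collecting PWV/A data. The CON and SMS session timetables in section 2.6 list VICORDER steps only as bfPWV/A, cfPWV/A and faPWV/A, or as all PWV/A measures. They contain no separate blood-pressure step. On the text, the brachial and central pressures therefore come from the steps that the limit governs.

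**2. What a cuff under that limit can register.** The premise is that a cuff can register a pressure P only if its inflation reaches P. The documents do not state this; it is a basic measurement principle. With inflation below 65 mmHg:

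- SBP can be read only if SBP < 65 mmHg, which is not expected in a healthy adult.
- DBP can be read only if DBP < 65 mmHg. A lower diastolic value is not excluded, but any value of 65 mmHg or more is.

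As illustration only, the sample LabChart export under Devices 7 & 8 shows values under its mean arterial pressure heading from about 80.0 to 108.5 mmHg. Systolic pressure is higher than mean pressure. That table is broken in the text, so no weight rests on it.

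**3. Central pressure.** A waveform can be recorded at low cuff pressure, so its shape is obtainable. Expressing it in mmHg requires calibration to known pressures, and the plan describes no calibration source outside the VICORDER brachial recording.

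**4. Other sources.** The only other pressure device is the finger NIBP. Tables 2 and 3 assign it baroreflex sensitivity, heart rate variability and heart rate. They do not assign it SBP/DBP or the calibration of central pressure.

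**5. Count, from Tables 2 and 3.**

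- Time points per completer: 7 (CON) + 8 (SMS) = 15.
- If all 20 participants complete: 15 × 20 = 300 peripheral sets and 300 central sets.
- Table 3 sets a triplicate rule against the VICORDER block. If it applies to blood pressure, the counts become 15 × 3 = 45 per completer and 45 × 20 = 900. The documents do not settle this.

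**6. What is not affected.** Brachial-femoral, carotid-femoral and femoral-ankle PWV rest on path length and transit time between waveforms, which need no pressure reading. Brain PWV comes from the transcranial Doppler. Augmentation index is a percentage of pulse pressure and need not be affected.

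**The case against.** The strongest reply is that the limit was meant only for waveform capture. It follows a sentence on PWV/A collection, the risk listed beneath it concerns the carotid site, and Device 1 ties sub-systolic inflation to detecting the waveform while describing brachial pressures in a separate entry. This reading is plausible. It does not remove the problem: section 6.1 would then state a ceiling that the scheduled brachial readings exceed, without mentioning those readings. Nor is the scope explicit, since PWV/A includes pulse wave analysis and the timetables show no separate pressure step.

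It is also fair to say that the affected outcomes are not primary. Peripheral pressures are mechanistic, and section 4.2 uses mechanistic outcomes to support discussion. Central pressures are secondary in only two of the four places where outcomes are listed. No power figure or decision rule changes.

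Some stronger readings are tempting but not supported:

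- **That 15 is the most inflations a participant could undergo above the limit.** It is a count of time points, and the triplicate rule may raise the number of inflations.
- **That inflating further would breach section 9.3, which requires conduct as described.** Taking brachial pressure with the VICORDER is itself described, so this presupposes which passage governs.
- **That no pressure could be read at all.** A diastolic pressure below 65 mmHg is not excluded by the limit.
- **That the finger device can simply take over.** The documents place the VICORDER brachial recording on the non-dominant arm and strap the finger device to the non-dominant wrist, so a brachial inflation may disturb its signal. Nothing says that the VICORDER accepts calibration from it.

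**Conclusion.** The inconsistency is real and should be corrected. As written, either brachial SBP/DBP and central pressures cannot be obtained as planned, or section 6.1 states a ceiling that scheduled measurements exceed and leaves those inflations out of its risk text. It touches every scheduled peripheral and central pressure set: 15 time points per completer, 300 of each if all 20 complete, before any triplicates. No PWV outcome is affected, so the two primary comparisons stand.

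The conclusion rests on three assumptions: a cuff must reach a pressure to register it; healthy adults have systolic pressures above 65 mmHg; and no calibration source exists beyond those the text names. The figures and the consent form were not available for this check, so what participants are told about cuff pressure is not judged. Nor does this point say which cuff pressure is right.

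**What to change.** Reconcile section 6.1, the Device 1 entries in sections 2.5 and 3, and Tables 2 and 3:

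- State in section 6.1 and in the Device 1 section which VICORDER uses the limit covers, treating the carotid balloon, PWV and pulse-wave capture, and brachial blood pressure separately.
- Make the risk text match every inflation that is actually scheduled.
- Name the source of SBP/DBP and the calibration of central pressures, consistently with that statement, and show the step in the session timetables.
- Say whether the triplicate rule applies to blood pressure.
- While amending, give central pressures the same role in the synopsis, Table 1, Table 2 and section 4.1.

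The cost is a wording amendment with matching IRB risk text. If the limit turns out to hold for every use, the source of these pressures has to be redefined, or the outcomes dropped, before data collection.
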